Using a stepped wedge cluster randomized design, 60 social network sub-groups of adults (30 Hispanic, 30Somali) with approximately 480 participants (approximately 7 per group) will be randomly assigned to receive the intervention either immediately or after a delay of one year. The intervention will consist of 12 community-based mentoring and education sessions and group activities, followed by 12 maintenance sessions delivered by trained Somali and Hispanic interventionists to members of their groups in a face-to-face or virtual format. Outcomes measured at baseline, 6 months, 12 months, and 24 months, will be derived from the American Heart Association's "Life's Simple 7": BMI and waist circumference (primary outcomes), blood pressure, fasting blood glucose, total cholesterol, physical activity level, dietary quality, and health-related quality of life. We will also test potential mediators of treatment effect consistent with the C2DREAM conceptual model.

The expected product will be a CBPR-derived, social network-informed intervention to reduce cardiovascular risk among two immigrant groups. The proposed study is innovative; it will be the first to evaluate a social network health promotion intervention among immigrant populations. Given that over one million immigrants arrive in the US annually, the potential public health impact of this work is considerable.

Preliminary Data

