Demographic, acculturation, and structural racism measures. The following demographic data will be collected at baseline: age, gender, ethnicity, country of birth, annual household income, education level, employment status, and use of social media. Participants will report on the following proxies for acculturation: years lived in the US, primary language spoken at home, and level of English language proficiency on a 5-point Likert scale.¹⁴⁴ Degree of dietary acculturation¹⁴⁵ will be assessed from results of 24-hour dietary recall described below. The following measures of structural racism will be obtained at baseline: Home address for automated collection of geolocation-based measures (Minnesota Measure of Structural Racism [MMSR], Area Deprivation Index [ADI], County Structural Racism Index); Everyday Racism Scale, Discrimination in Medical Settings Scale, and Medical Mistrust Scale.

Primary outcome measures.

BMI: Weight will be measured to the nearest 0.1 kg using a portable scale (Seca 880 Digital Floor Scale). Height will be measured to the nearest 0.1 cm at baseline only using a stadiometer. Participants will be asked to remove shoes prior to both measurements. BMI is calculated as weight (kg)/height squared (m²). Waist circumference will be measured to the nearest 0.1 cm at the narrowest part of the torso between the ribs and the iliac crest. Participants will remove excess clothing prior to the measurement and smooth the remaining clothing against the skin. Two measurements will be taken; if the difference between the two measures is more than 2.0 cm, a third measurement will be taken. The average of the two closest measures will be used.

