Social network sub-groups are sufficiently discrete for randomization: Our social network data analysis determined that these communities were composed of enough discrete sub-groups for randomization. An example of this is that the Hispanic network had 144 unique sub-groups. When considering only sub-groups composed of five or more individuals, there were still 88 sub-groups identified using modularity calculations. This is a sufficient number of sub-networks for randomization, especially when considering the approximately equal number of Somali networks. Therefore, the high clustering observed in our preliminary data, as demonstrated by the high modularity of the networks, indicates that there are clearly distinct subgroups in the networks and that randomization via subgroups is feasible and appropriate for the study.

Sample size considerations

Stepped wedge cluster randomization trials typically have more statistical power than other cluster randomized designs.¹¹⁵ This is because each cluster is able to serve as its own control, accounting directly for the within cluster correlation of outcomes. In addition, the impact of intra-cluster correlation on power is typically smaller than on conventional cluster randomized trials.¹⁷¹ For the current study, we expect each HP to recruit 6 to 8 participants, so assume 7 per cluster and a substantial loss to follow up of 20% over 12 months. We assume a conservative intra-cluster correlation in outcomes of 0.10 to calculate the design effect DE_{sw} based on the formula:^{115,171}

$$DE_{sw} = \frac{1 + \rho(ktn + bn - 1)}{1 + \rho \left(\frac{1}{2}km + bn - 1 \right)} \cdot \frac{3(1 - \rho)}{2t \left(k - \frac{1}{k} \right)}$$

where $k = 2$ is the number of steps (including baseline), $b = 1$ is the number of measurements per subject in the baseline step, $t = 1$ is the number of measurements per subject at each step, and $n=7$ is the number of subjects per cluster. Assuming 80% follow up and equal

distribution across clusters, and a 80% power, we estimate the detectable standardized effects (SDs) for a range of numbers of enrolled HPs with a maximum probability of a Type II error of 0.05.

SD	HPs	N total
0.1	478	1673
0.2	120	420

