0.3 53 187 For the primary endpoints, a third standard deviation (0.3SD) difference between groups will be considered clinically meaningful.¹⁷² On the basis of the previous Healthy Immigrant Families study, we will assume a 0.1 standard deviation change in the control group ("contamination") so this represents a 0.4SD change in the intervention group. Therefore, the study will accrue 54 clusters (27 per group) with approximately seven participants in each cluster, for a total sample size of approximately 378 network participants.

Data Analysis

All analyses will be appropriate for stepped wedge trials. In the direct effects model, the co-primary endpoints will be changes in BMI and waist circumference from baseline to month 12 and the 12-month change in the Ajzen TPB, the common outcome for C2DREAM. We will use mixed effects regression models to adjust for correlations within social network clusters and over time.¹¹⁴ Models will include indicators for intervention status, step, and their interaction. Covariates indicated above including demographics (e.g., sex, years since arrival to the US) and social covariates will be included in profile analysis models to assess the sensitivity of the primary analysis conditional on these potential concomitant (mediating) influences. All secondary endpoints will be analyzed using the same methods as used for the primary endpoints.

Missing data will be handled in several ways using an extensive library of macro procedures designed specifically for such tasks by the Mayo Clinic Division of Biostatistics.¹⁷³ Simple imputation methods such as minimum, average, or maximum values carried forward will be followed by multiple imputation methods to assess the robustness of the study results in the presence of the missing data. All models will be assessed for goodness of fit, with effects reported with confidence intervals. All hypothesis tests will use $\alpha = 0.05$ to determine significance.

Bibliography

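### Two primary outcomes in one part of the plan, three in another, and no rule for which results make the trial positive

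*Combined protocol and SAP*

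**What the plan says.** **Two primary outcomes.** Specific Aims labels "BMI and waist circumference (primary outcomes" and lists the other measures after them. Under Measures, the paragraph headed "Primary outcome measures" describes how BMI and waist circumference are measured and nothing else. Hypothesis 1 names the same pair, joined by *and*, without calling them primary.

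**Three co-primary endpoints.** Data Analysis states that "the co-primary endpoints will be changes in BMI and waist circumference from baseline to month 12 and the 12-month change in the Ajzen TPB", and describes the last only as "the common outcome for C2DREAM". The acronym is not expanded. Theory-based measures covers self-efficacy, social support, group cohesion and weight-loss norms, but does not combine them into a TPB score. Elsewhere C2DREAM is a conceptual model, and Specific Aims links it to mediators: "We will also test potential mediators of treatment effect consistent with the C2DREAM conceptual model".

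**Error rate and power.** Data Analysis says "All hypothesis tests will use $\alpha = 0.05$ to determine significance". It gives no hierarchy, adjustment or any-versus-all rule, and does not state sidedness. Sample size considerations gives one power figure ("and a 80% power, we estimate the detectable standardized effects (SDs") and one effect size: "For the primary endpoints, a third standard deviation (0.3SD) difference between groups will be considered clinically meaningful".

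Month 12 as the primary time point is the same in Measures and Data Analysis and is not in question.

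**The concern.** The sections disagree on what decides the trial. The same data could be judged on two endpoints or three, under a rule that all must succeed or a rule that one suffices, and the text excludes none of these. The choice could then be made after the results are known.

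The two rules have different costs, and these are alternatives that do not add up. If all must succeed, testing each at 0.05 is valid, but the probability of a positive trial is below the power of any single endpoint. If one suffices, unadjusted testing at 0.05 puts the family-wise error above 5%. Under neither rule do the stated 0.05 and 80% both describe trial success. Reporting effects with confidence intervals, as planned, shows the results but does not settle the claim.

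**Working it through.** **1. The plan's own power figure.** Inputs from Sample size considerations: effect 0.3 SD, ICC 0.10, n = 7 per cluster, 20% loss, k = 2, b = 1, t = 1, 80% power. Alpha 0.05 comes from Data Analysis; two-sided is my assumption. I read the printed km in the design-effect formula as ktn.

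- Design effect = [1 + 0.1(14 + 7 − 1)] / [1 + 0.1(7 + 7 − 1)] × 3(0.9) / [2(2 − 0.5)] = (3.0 / 2.3) × 0.9 = 1.174.
- Individually randomised total: 175 per arm, 350 in all. 350 × 1.174 = 411, or 59 clusters of 7. With 20% loss, 411 / 0.8 = 514, or 74 clusters.
- The plan's table gives 53 clusters, and the text 54. This is not reproduced.
- Power at 54 clusters, no loss: 378 / 1.174 = 322, or 161 per arm. 0.3 × √(161/2) = 2.69, giving 76.8%.
- Power at 54 clusters, 20% loss (n = 5.6, design effect 1.150): 302.4 / 1.150 = 263, or 131.5 per arm. 0.3 × √(131.5/2) = 2.43, giving 68.2%. One-sided 0.05 with the same loss gives 78.5%.

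The same sentence of the plan also prints a Type II error of 0.05, which conflicts with 80% power. The 80% below is therefore taken at face value, for illustration only.

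**2. If all must succeed.** The test statistics are treated as multivariate normal, each with mean 1.96 + 0.84 = 2.80 (80% power), and joint power is the probability that all exceed 1.96. The documents give no correlations. I assume 0.3, 0.6, 0.8 or 0.9 for BMI with waist, and 0 or 0.3 for TPB with each of them.

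| BMI-waist correlation | 0.3 | 0.6 | 0.8 | 0.9 |
|---|---|---|---|---|
| Two endpoints | 67% | 70% | 73% | 75% |
| Three, TPB correlation 0 | 53% | 56% | 58% | 60% |
| Three, TPB correlation 0.3 | 57% | 59% | 61% | 63% |

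Hand check under independence: 0.8² = 64% and 0.8³ = 51%, just below the table as expected.

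**3. Cluster count.** Specific Aims and Study Design plan 60 groups, not 54. If 54 gave 80% and information scales with clusters, the mean becomes 2.80 × √(60/54) = 2.95. Power per endpoint is then about 84%, and two-endpoint joint power about 73-80% over the same correlations.

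**4. If any one suffices.** Family-wise error, two-sided, counting a false result in either direction:

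| BMI-waist correlation | 0.3 | 0.6 | 0.8 | 0.9 |
|---|---|---|---|---|
| Two endpoints | 9.5% | 8.8% | 7.8% | 7.0% |
| Three, TPB correlation 0 | 14.0% | 13.3% | 12.4% | 11.7% |
| Three, TPB correlation 0.3 | 13.6% | 13.0% | 12.1% | 11.4% |

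Hand check under independence: 1 − 0.95² = 9.75% and 1 − 0.95³ = 14.3%.

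**The case against.** **The wording already implies a rule.** The term co-primary, and the *and* in Hypothesis 1, point to all endpoints having to succeed. This is the better reading, and under it no alpha adjustment is needed. A reader who sees three endpoints each tested at 0.05 might infer that the trial inflates its type I error; the documents do not support that as a finding. What stands is that no sentence states the rule, the list it would apply to differs between sections, and the 80% is not the probability of success on all of them.

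**The TPB endpoint may be defined elsewhere.** The reference to a common outcome suggests a consortium definition, which these documents neither contain nor cite. A reader might also infer that its visits are undefined. That goes too far: Data Analysis specifies a 12-month change, and Measures has participants complete a survey at 0, 6, 12 and 24 months. If TPB is a survey measure, its visits follow. Instrument, scoring and direction of benefit are still missing.

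**The numbers rest on assumptions.** This is fair. The correlations are assumed, and 80% is not reproduced. At 68.2% per endpoint, two-endpoint joint power would be about 50-62%. Equal power for TPB is also a guess: with BMI-waist correlation 0.8 and TPB uncorrelated, TPB power of 50% or 95% gives 0.729 × 0.50 = 36% or 0.729 × 0.95 = 69%, instead of 58%. So the tables show direction and rough size only. In particular, they do not support an exact number of extra clusters, especially with 54 and 60 both planned.

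**Conclusion.** The point holds. The plan names two primary outcomes in two sections and three in another, leaves the third without instrument, scoring or direction of benefit, and states no success rule. This is a contradiction about what decides the trial, and goes beyond missing detail.

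If all must succeed, the more natural reading, error control is intact and the shortfall is in power. With 80% per endpoint at 54 clusters taken at face value and BMI-waist correlation 0.3 to 0.9, joint power is about 67-75% for two endpoints and 53-63% for three; with 60 clusters it is about 73-80% for two. If one suffices, two-sided family-wise error is about 7-10% for two endpoints and 11-14% for three. The contradiction and the missing rule do not depend on these figures.

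A reader might conclude that the trial is too small and must enrol more. That does not follow from this point, because a fixed sequence or an honestly stated joint power resolves it without more participants.

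**What to change.** Use one primary list in Specific Aims, Measures and Data Analysis, and state one success rule before outcome data are examined. Two options:

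- **Fixed sequence at two-sided 0.05**, for example BMI, then waist circumference, with TPB secondary or last. The order is the sponsor's choice. The first endpoint keeps the full alpha and whatever power the design really has. The cost is that no formal claim can be made on later endpoints if an earlier one fails.
- **All must succeed.** Say so, keep each test at 0.05, and restate the power as joint power with its assumed correlations. The cost is a lower stated chance of success. This calls for restating the power, not for more enrolment.

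In either case, state sidedness and say which cluster count, 54 or 60, the power refers to. If TPB stays in the primary set, give its instrument, scoring and direction of benefit under Measures, or cite the C2DREAM document that defines them. All of this is wording, with no new participants or visits, provided TPB is already among the baseline and 12-month survey measures.

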Table 2: Biometric and health behavior measures before and after the intervention (N=39)

	Baseline	Week 12	P value
Weight, kg (SD)	91.6 (15.9)	89.7 (16.6)	< 0.0001
Servings of fruit per day (SD)	1.7 (1.0)	2.9 (2.1)	0.013
Servings of vegetables per day (SD)	1.9 (1.2)	2.6 (1.4)	0.009
Fruits and vegetables as snacks ^a (SD)	2.4 (0.9)	3.0 (0.8)	0.001
Regular soda drinks ^b (SD)	1.6 (0.7)	1.3 (0.4)	0.003
Fruit drinks, punch, or sports drinks ^c (SD)	1.7 (0.8)	1.5 (0.6)	0.10
Total MET-minutes per week ^d (SD)	2689.5 (3230.8)	6595.1 (7371.6)	0.02
Systolic blood pressure, mm Hg (SD)	133.9 (16.9)	127.2 (15.8)	0.001
Diastolic blood pressure, mm Hg (SD)	81.0 (9.5)	75.8 (9.6)	< 0.0001
Waist circumference, cm (SD)	102.3 (13.7)	100.6 (12.3)	0.14
Glucose, mg/dL (SD)	90.4 (18.4)	91.9 (11.1)	0.73
Total Cholesterol, mg/dL (SD)	205.1 (49.4)	190.8 (50.1)	0.02
Triglycerides, mg/dL (SD)	206.1 (175.0)	130.1 (78.6)	0.001

^a4-point Likert scale of frequency in response to, "Do you eat fruits and vegetables as snacks?"

^b4-point Likert scale of frequency in response to, "Do you drink regular soda?"

^c4-point Likert scale of frequency in response to, "Do you drink fruit drinks, punch, or sport drinks?"

^dEnergy expended from carrying out physical activity as measured by the International Physical Activity Questionnaire

Study Design and Procedures

Aim #1: Conduct a randomized trial to assess the efficacy of a social network-informed CBPR-derived health promotion intervention on obesity and other measures of cardiovascular risk in two immigrant communities.

Overview. The first aim address stages II-III of established methods for behavioral intervention research.¹¹⁰ Using a stepped wedge cluster randomized design, 60 social network-based groups (30 Hispanic, 30 Somali; each group with approximately 7 participants) will be randomly assigned (stratified by ethnicity, HP sex, and network size) to receive the intervention either immediately (step 1) or after a delay of one year (step 2). Outcomes, measured at baseline, 6 months, 12 months, and 24 months, will be derived from the American Heart

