Association's "Life's Simple 7": BMI and waist circumference, blood pressure, fasting blood glucose, total cholesterol, physical activity level, and dietary quality. We will also measure quality of life and potential mediators of treatment effect consistent with our theoretical framework. The intervention will consist of community-based mentoring and education sessions, group activities, and application of a community toolkit for healthy weight loss delivered by trained HPs from Hispanic and Somali communities to their social networks. During the control period, participants will receive printed health information developed by the study team during each assessment that is not directly related to diet or weight loss.

Figure 1. Study Design and Intervention Schedule

Month	0	0	0-5	6	6-11	12	12-18	18-23	24
Intervention Group	Baseline Measures	Randomization	12 peer-led, face-to-face or virtual group-based sessions • Goal setting • Tracking of physical activity and diet • Educational content • Positive reflections	6-Month Measures	12 peer-led, face-to-face or virtual group-based sessions • Goal setting • Tracking of physical activity and diet • Positive reflections	12-Month Measures	Sustainability Phase No Organized Intervention	Sustainability Phase No Organized Intervention	24-Month Measures
			No Intervention		No intervention		12 peer-led, face-to-face or virtual group-based sessions • Goal setting • Tracking of physical activity and diet • Educational content • Positive reflections	12 peer-led, face-to-face or virtual group-based sessions • Goal setting • Tracking of physical activity and diet • Positive reflections	

Blinding. Study staff performing measurements and data analysis as well as all named investigators will be blinded to treatment condition.

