Rationale for stepped wedge design. While randomized trials lend maximal validity to study design, the use of control groups in CBPR is problematic in that it may be perceived as withholding of resources that the community helped to create.^{32,111} Therefore, delayed-intervention control groups are frequently used in CBPR contexts.^{112,113} One potential concern with a delayed intervention is differential attrition in control versus intervention arms. However, our prior randomized controlled trial that used the same design found high rates of retention in both study groups over a two-year period (above). In addition, stepped-wedge designs provide increased protection from bias by incorporating both historic and contemporaneous controls, as well as increased statistical power when there is positive within cluster correlation of outcomes over time.^{114,115}

Rationale for social network intervention. In the HIF study, the intervention was delivered to individual Hispanic and Somali families. Participants noted in post-intervention focus groups that a more flexible group-based approach with friends and family may promote greater participation. After reviewing these data in meetings and an RHCP research summit, community and academic partners embraced the conceptual pivot from an intervention delivered among a subset of individuals to an intervention delivered through social networks. Community partners reported this approach as highly acceptable since social network effects are perceived as influential on health behaviors in Hispanic and Somali communities. On the basis of these discussions, the social network analysis conducted by RHCP among 1,301 participants confirmed the influence of obesogenic social network effects in these populations. The subsequent pilot social network intervention was highly successful and enthusiastically received by participants in post-intervention focus groups.

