The programmatic intervention dose is lower than many health promotion interventions. The rationale is that 1) the intervention will be more impactful when delivered by a member of participant's social network,¹³⁸ and 2) non-programmatic health promoting activities and interactions are likely to occur within and between social networks (indirect intervention effect) throughout the study interval.¹³⁹ This approach highlights the potential advantages of social network interventions for scalability and sustainability.^{70,140}

The rationale for the mentorship and education component of the intervention arose from the success of this model in the Healthy Immigrant Families study, where the interventionists were not necessarily members of participant's social networks. For this application, mentorship has the potential to carry more influence through

delivery within social networks by respected peers. Peer mentoring has been shown to be effective in promotion of healthy eating and physical activity among groups with low socioeconomic position.^{141,142}

Treatment Fidelity & Measures

Treatment Fidelity

In the design and conduct of this study, we have incorporated recommendations from the Treatment Fidelity Workgroup.¹⁴³ We have recently described our process for assessing treatment fidelity for community-based behavior change interventions with immigrant groups in a CBPR framework.¹³⁶ The HPs will utilize a manual (phase 1) containing an outline/script for each session and a checklist of critical topics to be covered at each session. Study assistants, who were interventionists for the Healthy Immigrant Families study, will randomly observe 5% of sessions with the HPs. These study assistants have developed expertise as health behavior change interventionists through 250 hours of training followed by two years of intervention delivery.¹³⁶ They will be further trained in fidelity assessment for this study, thereby addressing the barrier of language concordance between interventionists and assessors. Bi-weekly meetings will be held with the HPs and study team to reinforce treatment fidelity, provide corrective feedback, and to conduct additional training if needed.

Measures

Data will be collected at 0 (baseline), 6, 12 (primary endpoint) and 24 months by trained study staff blinded to treatment condition. Participants will complete a survey and participate in physical measurements.

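### The co-primary month-12 comparison is completed before crossover, but the stated stepped-wedge model and sample-size formula do not fit it

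*Combined protocol and SAP*

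**What the plan says.** The Data Analysis section states that "the co-primary endpoints will be changes in BMI and waist circumference from baseline to month 12", and Measures labels month 12 as primary: "Data will be collected at 0 (baseline), 6, 12 (primary endpoint) and 24 months by trained study staff". The Overview under Study Design and Procedures randomises groups to start "either immediately (step 1) or after a delay of one year (step 2", so *step* there is the randomised arm. In Figure 1 the delayed groups have no sessions until after the month-12 measures. From month 12 to month 24 the immediate groups are in a "Sustainability Phase No Organized Intervention" period.

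The analysis text reads "All analyses will be appropriate for stepped wedge trials" and "Models will include indicators for intervention status, step, and their interaction". It does not define *step*, give the intervention-status code for the immediate arm in its second year, or name the coefficient that is the primary test.

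Two passages look beyond month 12. Rationale for stepped wedge design says that "stepped-wedge designs provide increased protection from bias by incorporating both historic and contemporaneous controls". Sample size considerations says that "each cluster is able to serve as its own control". The latter section uses a stepped-wedge design effect with k = 2, where k counts steps with baseline among them, so *step* there is a period. Its table gives 53 clusters for 0.3 SD, and the plan rounds this to 54.

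**The concern.** At month 12 no delayed cluster has crossed over, so the primary contrast has no stepped-wedge content. A model with status, step and their interaction is written for data that include the crossover. Delayed clusters can act as their own controls only if their month-24 data enter.

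The analyst must therefore either drop part of the stated model or add month 24 to an endpoint that stops at month 12. If month 24 is added, the result depends on what *step* means and on how the off-intervention year is coded. The same mismatch affects the sizing, because the power statement cannot be tied to the month-12 contrast.

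**Working it through.** **1. Can the stated model be fitted through month 12?** Use months 0 and 12, with status 0,1 in the immediate arm and 0,0 in the delayed arm. Status is 1 in one cell only, so the interaction column duplicates the status column.

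- *Step* = visit: 4 columns, rank 3. The month-12 arm difference survives; the interaction does not.
- *Step* = arm: 4 columns, rank 3. With no visit term, the surviving status coefficient is the immediate arm's own before–after change.

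**2. What if month 24 is added?** Take true means 0, 1, 1−d (immediate) and 0, 0, 1 (delayed) at months 0, 12 and 24. Here d is the share of effect lost by month 24, which is an assumption, and no secular trend is assumed. Let r be the between-visit correlation of cluster means. With ICC 0.10 and 5.6 retained per cluster, r = (0.1 + 0.9s/5.6)/(0.1 + 0.9/5.6), where s is the within-person share of the remaining variance. Assuming s = 0 gives r = 0.384; assuming s = 0.85 gives r = 0.908.

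- *Step* = visit, immediate arm kept at 1: rank 4 of 6. The model forces the arms equal at baseline and month 24, so the month-12 estimate is 1 − [r/(1+r)](0 − d) = 1 + d·r/(1+r). The factor r/(1+r) is 0.277 or 0.476.
- *Step* = visit, status returned to 0: rank 5 of 6, and only the baseline status term is lost. The month-12 estimate is 1.
- *Step* = arm, status kept at 1: rank 4 of 4. The immediate-arm coefficient averages months 12 and 24: [1 + (1−d)]/2 = 1 − d/2.
- *Step* = arm, status returned to 0: rank 4 of 4. Months 0 and 24 become the comparator: 1 − (1−d)/2.

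Ratio of estimate to true month-12 effect:

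| Step, status in months 12–24 | No loss | Half lost | All lost |
|---|---|---|---|
| Visit, kept at 1 | 1.00 | 1.14–1.24 | 1.28–1.48 |
| Visit, returned to 0 | 1.00 | 1.00 | 1.00 |
| Arm, kept at 1 | 1.00 | 0.75 | 0.50 |
| Arm, returned to 0 | 0.50 | 0.75 | 1.00 |

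On a true 0.3 SD, the first row gives 0.34–0.37 SD (half lost) or 0.38–0.44 SD (all lost). The third row gives 0.225 or 0.15 SD.

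**3. Does 53 clusters follow from the printed formula?** Inputs from Sample size considerations are k = 2, b = 1, t = 1, n = 7, ICC 0.10, 80% power and 20% loss (7 × 0.8 = 5.6). The effect is 0.3 SD. I read the undefined km in the denominator as ktn, and the 0.05 attached there to Type II error as alpha.

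- Design effect, n = 7: (1 + 0.1×20)/(1 + 0.1×13) × 2.7/3 = 3.0/2.3 × 0.9 = 1.174.
- Design effect, n = 5.6: 2.58/2.02 × 0.9 = 1.150.
- Unclustered total, two-sided: 4(1.960 + 0.842)²/0.3² = 348.8. One-sided: 4(1.645 + 0.842)²/0.3² = 274.8.

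| Alpha 0.05 | Clusters, no loss | Clusters, 5.6 retained | Power of 54, no loss | Power of 54, 5.6 retained |
|---|---|---|---|---|
| Two-sided | 348.8×1.174/7 = 58.5 | 348.8×1.150/5.6 = 71.6 | 77% | 68% |
| One-sided | 274.8×1.174/7 = 46.1 | 274.8×1.150/5.6 = 56.4 | 85% | 78% |

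Power is Φ(0.3/√(4·DE/(54n)) − z). None of the four combinations gives 53.

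**4. Which design does the formula describe?** The value 1.174 equals the generalised least squares variance for three occasions (0, 12, 24) with the immediate arm still coded as treated at month 24. With one step after baseline (k = 1), the factor k − 1/k is 0 and the formula is undefined. It therefore does not size the month-12 contrast.

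**5. Power for months 0 and 12.** With 54 clusters, 5.6 retained, two-sided alpha and baseline adjustment, the variance is (4/54)(0.1 + 0.9/5.6)(1 − r²). Power is 65% at r = 0.384, 70% at 0.5, 86% at 0.7 and over 99% at 0.9, if 0.3 SD is on the level scale. The plan gives no value for r.

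**The case against.** The best defence is that the endpoint wording already fixes the visits: a change from baseline to month 12 uses months 0 and 12, and the remarks on historic controls and on clusters as their own controls describe stepped-wedge designs in general. Under that reading, with *step* as visit, dropping the redundant interaction leaves the correct arm difference. The Blinding paragraph also keeps data analysts and named investigators unaware of treatment condition, which limits data-driven choice of coding. Both points stand, and they are why no bias is shown. They do not make the model sentence fit the endpoint or settle what *step* means.

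A reader might infer that the plan inflates the month-12 effect. The documents do not support that. Inflation needs month 24 added, *step* read as visit, the off-intervention year coded as treated, and a waning effect. Other versions the text permits give no bias or understatement.

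A reader might also infer that the trial is underpowered. That does not follow either. The formula ignores within-person correlation, which could raise power well above 80% (step 5 of the working). The plan does not state sidedness, and one-sided the shortfall with loss is small (56.4 clusters against 53). The design sections mention 60 groups rather than 54; under the same formula with loss, 60 gives 73% two-sided and 82% one-sided.

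**Conclusion.** The point stands as a mismatch between endpoint, model and sample size, and should be fixed. The rank result through month 12 needs no assumption about the data. The month-24 ratios run from 0.50 to 1.48, depending on assumed waning, on assumed correlation for the upper values, and on choices the plan leaves open; they show sensitivity, not an expected error. The sizing discrepancy rests on the stated inputs and the reading of km as ktn. With the stated 20% loss, it holds for both one-sided and two-sided alpha. Actual power for the month-12 contrast cannot be determined from the documents.

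**What to change.** Replace the model sentence for the primary analysis with a mixed model that uses data through month 12 only. Fixed effects are visit, randomised arm × visit and the stratification factors; random effects are cluster and participant. State that the primary estimate for each co-primary outcome is the arm difference in change from baseline to month 12, with its 95% CI. Reconcile the stratification factors first: Randomization lists health promoter age and the Overview does not.

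Analyse month 24 separately, with an explicit status code for the sustainability year. Define *step* once. Restate power for the month-12 contrast, giving sidedness, SD scale (level or change), assumed within-person correlation and retained cluster size.

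A common baseline mean (defensible because randomisation follows baseline), cluster-by-visit effects and an unstructured covariance are optional refinements.

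The cost is text and a new power calculation; visits and data collection are unchanged. Month 24 would add no precision to the primary estimate, and the stated power may change.
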